1.3.2 Combining Immunotherapy with Radiation Therapy

Radiation therapy remains a backbone in the treatment of HNSCC in definitive, palliative, and adjuvant setting. The rationale for postoperative radiation is to target microscopic deposits of cancer cells that may remain after resection [20]. If untreated, these cells may eventually lead to a local-regional recurrence. Immunologically, radiotherapy induces antigen release from the tumor and danger signals activating both the host's innate and adaptive immune system [21]. This may lead to reverse the tolerance to weakly immunogenic tumor-associated antigens and elicit both local and distant anticancer immune response.

Radiation therapy has been shown to have a synergistic effect with various immunomodulating agents [22]. Additionally upregulation of PD-L1 expression leads to T cell exhaustion, which causes resistance to treatment from radiotherapy [23]. This provides a rationale for the combination of PD-L1 inhibitors with radiation therapy and is currently being evaluated in multiple clinical trials.

1.4 PD1 and PDL1 inhibition in metastatic/recurrent HNSCC

Immunotherapy has made substantial advances in the care of incurable HNSCC, with the recent FDA approval of the immune checkpoint inhibitors pembrolizumab and nivolumab in the second-line setting for patients with disease progression or recurrence after first line platinum-based chemotherapy. In phase II study, response rate (RR) to pembrolizumab in unselected and mostly highly pretreated patients

was 16% and overall survival (OS) was 8 months, results significantly superior to that expected with standard therapy [24]. Nivolumab was compared in phase III study to standard of care treatment with investigator's choice of docetaxel, methotrexate or cetuximab and showed superior survival [25]. Durvalumab was evaluated in 62 patients with recurrent or metastatic HNSCC and had an overall response rate of 12% [26]. Of note, in each of these studies, the toxicity profile of immunotherapy was notably superior to that seen in major studies of cisplatin. Critically for consideration of these agents in the adjuvant context, survival advantages seen in these studies and in clinical practice include a real proportion of long-term survivors.

1.5 Study Agent

1.5.1 Durvalumab

Durvalumab is a human monoclonal antibody (mAb) of the immunoglobulin G (IgG) 1 kappa subclass that blocks the interaction of PD-L1 (but not programmed cell death ligand-2) with PD-1 on T cells and CD80 (B7.1) on immune cells. Durvalumab has been engineered to reduce antibody-dependent cellular cytotoxicity and complement-dependent cytotoxicity. *In vitro* studies demonstrate that durvalumab antagonizes the inhibitory effect of PD-L1 on primary human T cells, resulting in their restored proliferation and release of interferon gamma.

As of July 2019, 5127 patients have been exposed to one or more doses of durvalumab in ongoing open-label AstraZeneca-sponsored or MedImmune-sponsored Phase I-III monotherapy and combination therapy studies across all indications [27].

In patients with recurrent/metastatic HNSCC who received durvalumab monotherapy from Study 1108, overall response rate (ORR) was 7.3% across all patients, 16.7% in patients with PD-L1 high tumors and 2.7% in patients with PD-L1 low/negative tumors. Median OS was 8.4 months and OS at 24 months was 24.2%. In Study D413C0001, HNSCC patients with PD-L1% high, ORR was 16.2%. The median duration of treatment was 3.45 months, while the median OS was 7.1 months [24].

1.5.1.1 Rationale for Fixed Dosing of Durvalumab

A population pharmacokinetic (PK) model was developed for durvalumab using monotherapy data from a Phase I study (study 1108; N=292; doses=0.1 to 10 mg/kg once every 2 weeks (Q2W) or 15 mg/kg once every 3 weeks (Q3W); solid tumors). Population PK analysis indicated only minor impact of body weight (WT) on the PK of durvalumab (coefficient of ≤ 0.5). The impact of body WT-based (10 mg/kg Q2W) and fixed dosing (750 mg Q2W) of durvalumab was evaluated by comparing predicted steady state PK concentrations (5th, median and 95th percentiles) using the population PK model. A fixed dose of 750 mg was selected to approximate 10 mg/kg (based on median body WT of ~75 kg). A total of 1000 patients were simulated using body WT distribution of 40–120 kg.

Simulation results demonstrate that body WT-based and fixed dosing regimens yield similar median steady state PK concentrations with slightly less overall between-patient variability with fixed dosing regimen.

A fixed dosing approach is preferred due to ease of use and reduced dosing errors. Given expectation of similar pharmacokinetic exposure and variability, we considered it feasible to switch to fixed dosing regimens. Based on average body WT of 75 kg, a fixed dose of 1500 mg durvalumab (equivalent to 20 mg/kg) will be used at Q3W during cycles 1-3 and Q4W during cycles 4-6 in the current study.

1.5.1.2 Durvalumab Dosing Schedule

Pre-clinical and clinical studies have evaluated the scheduling of durvalumab at two week, three week, and four week cycles. We have decided to proceed with durvalumab Q3W cycles when used in combination with radiation therapy and then Q4W when used as monotherapy following the completion of radiation.

1.5.2 Radiation Therapy + Durvalumab

In a single center subset of patients with solid malignancies, a phase I/II trial of durvalumab in combination with radiotherapy in the palliative setting was shown to be safe. The median duration of exposure to durvalumab was 5.2 months with a median delivery of 11 cycles (range, 4-38 cycles). RT (conformal 3D RT, 79% and intracranial stereotactic RT, 21%) was delivered at 28 Gy (range, 6-92), in a median number of five fractions (range, 1-10) and over a median duration of 6 days (range, 1-14). Five patients (50%) reported an irradiation-related adverse event grade 1 or 2 and one patient had two grade 2 AEs. The most frequently reported AE was grade 2 mucositis. There were no grade three or higher AEs.

1.6 Rationale for Clinical Study

The rationale for combining immuno-oncology (IO) with radiotherapy is multifactorial. In addition to cell death caused by high-dose radiation, radiotherapy has crosstalk with the immune system in three principle ways: (1) induction of immunogenic cell death to recruit antitumor T cells to the irradiated site; (2) upregulation of major histocompatibility complex (MHC) I expression, which was previously downregulated for immune escape; and (3) expansion of the diversity of the T cell receptor (TCR) repertoire to detect tumor antigens [28].

Therefore, the combination of PD-1/PD-L1 inhibitors and radiotherapy has the potential for synergistic properties by (1) reducing the number of MDSCs in the tumor microenvironment; (2) increasing CD8+ to Treg ratio; and (3) enhancing CD8+ infiltration, thereby augmenting the antitumor response. There currently exists data in multiple tumor types showing the positive role of combining PD-1/PD-L1 inhibitors and radiotherapy in different types of tumors.

1.6.1 Dose Rationale

Durvalumab dosing at 1500mg IV q3 and q4 weeks has been previously studied and has minimal toxicities when combined with radiation therapy. The use of 2 Gy over 30 fractions totaling a final dose of 60 Gy is the standard radiation dosing regimen in the adjuvant setting.

1.7 Correlative Studies

The tumor immune microenvironment is a complex mixture of competing cellular phenotypes. Thus, an optimal predictor of response to immunomodulatory therapy will likely include features that describe tumor genetics, tumor-related immunosuppression, and any existent but insufficient anti-tumor immune response. Chronic antigen exposure in the setting of tumor growth and metastasis leads to anergy and dysfunction (exhaustion) of the adaptive immune response, in part through increased engagement of the PD-1 receptor with its ligand (PD-L1). The net result of signaling through this axis is an attenuation of the cytotoxic and cytokine-producing capacity of tumor-infiltrating lymphocytes, leading to ineffective antitumor immune responses. In patients with metastatic melanoma, the fraction of partially exhausted cytotoxic T lymphocytes (peCTLs, tumor-infiltrating CD8+ T cells expressing high levels of cytotoxic T lymphocyte-associated antigen 4 [CTLA-4] and PD-1) strongly correlates with response to anti-PD-1 monotherapy. We plan to assess these parameters in our proposed study.

We hope to characterize the tumor immune microenvironment in multiple settings (1) in pre-treatment, surgically resected tissue, (2) during various times points during treatment with combination IO therapy with radiation therapy, and (3) at time of disease recurrence. Correlative studies will be run in both tumor and blood samples.

Specific aims include: (1) evaluation of the immunosuppressive biomarker PD-L1 on tumor and immune cells using immunohistochemistry analysis at pre-treatment and at disease recurrence. The expression of baseline PD-L1 levels will be assessed for its predictive response to recurrence; and (2) measurement of inflammatory/immune signature including CD4, CD8, CD25, FOXP3 and TUNEL/Caspase3 by flow cytometry to better understand the treatment-related changes in the tumor microenvironment.

2.0 STUDY OBJECTIVES

2.1 Primary Objective

2.1.1 To estimate median 3-year disease free survival (DFS) in patients with intermediate-risk HNSCC treated with adjuvant durvalumab with radiotherapy.

2.2 Secondary Objectives

- 2.2.1 To characterize safety by evaluating Grade 3-4 acute toxicities of adjuvant durvalumab with radiotherapy in intermediate-risk HNSCC patients
- 2.2.2 To characterize the Grade 3-4 chronic toxicities of adjuvant durvalumab with radiotherapy in intermediate-risk HNSCC patients.
- 2.2.3 To characterize any-grade chronic toxicities of adjuvant durvalumab with radiotherapy in intermediate-risk HNSCC patients.
- 2.2.4 To estimate median OS in patients with intermediate-risk HNSCC treated with adjuvant durvalumab with radiotherapy.
- 2.2.5 To correlate PD-L1 expression with disease free survival

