3.0 Criteria for Evaluation / Study Endpoints

3.1 Primary Endpoint

- 3.1.1 3-year DFS will be estimated via the Kaplan-Meier method. DFS is defined as the time from D1 of treatment to time of disease recurrence or death.

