3.2 Secondary Endpoints

- 3.2.1 Grade 3-5 acute toxicity will be evaluated according to guidelines from NCI CTCAE, v5.0 and include toxicity from the first day of treatment with immunotherapy until 30 days after completion of concurrent immunotherapy and radiation. Toxicity will include all toxicity attributed to the total study regimen (inclusive of radiation) not just to durvalumab alone.
- 3.2.2 Grade chronic 3-5 toxicity will be evaluated according to guidelines from NCI CTCAE, v5.0 and include toxicity continuing or occurring 30 days after completion of concurrent immunotherapy and radiation, and will be followed for up to 6 months.
- 3.2.3 OS will be estimated via the Kaplan-Meier method. OS is defined as the time from D1 of treatment to death from any cause.

3.2.4 Measure PD-LI expression by immunohistochemistry. Pre-treatment PD-L1 expression will be correlated with disease free survival following treatment of adjuvant durvalumab with radiotherapy

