5.9 Duration of Follow Up

All patients will be followed for up to 5 years, or until death, whichever occurs first after removal from study treatment for determination of study endpoints. Patients removed from study treatment for unacceptable AEs will be followed for resolution or stabilization of the adverse event(s). All patients (including those withdrawn for AEs) should be followed after removal from study treatment as stipulated in the protocol.

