9.2 Sample Size, Accrual and Duration of Accrual

Our evaluable study sample size (N_{total}) is 17, and we will enroll 18 to allow for possible non-evaluable patients. Based on a historical control of 10yr DFS is 19% (Cooper, RTOG 1016), the 3 year DFS is approximated to be 60.8%. Based on this calculation, we will need a sample size of 17 patients, to detect a 23% difference in 3 year DFS with 80% power (table below) and one-sided alpha of 0.1.

Difference from Historical Control	10%	20%	23%	25%
Test significance level, α	0.050	0.050	0.010	0.050
1 or 2 sided test?	1	1	1	1
Null hypothesis proportion, π_0	0.608	0.608	0.608	0.608
Alternative proportion, π_A	0.708	0.808	0.838	0.858
Power (%)	80	80	80	80
n	141	33	17	20

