9.3 Data Analysis Plans

Analytic plan for secondary objective:

The rate of grade 3-5 acute toxicity will be tabulated as described above to determine whether the criterion for safety has been met. A confidence interval for this rate will be calculated based on the methods of Koyoma T, and Chen H. Rates of individual types/grades of toxicities will also be reported [30].

Median DFS will be estimated using the Kaplan Meier method.

Analytic plan for additional secondary objective:

1. Grade 3-5 chronic toxicities will be tabulated by type and grade.
2. Median OS will be estimated using the Kaplan Meier method.
3. PD-L1 expression will be measured from baseline tumor sample using IHC. Expression will be correlated with DFS using the Kaplan Meier method. A

Log-rank test will compare DFS between those with and without PD-L1 expression.

Analytic plan for exploratory Objectives:

1. HPV status will be measured per institutional SOC, typically p16 and/or HPV FISH. The Kaplan Meier method will be used and a Log-rank test will compare DFS between HPV positive/negative patients.
2. Tumor infiltrating level (TIL) expression will be measured by flow cytometry at baseline and if possible at tumor recurrence. These levels will be compared at these time points using paired t-tests (pre vs final post assessment) or longitudinal models that account for repeated assessments when available. These models can be broadened to allow for comparisons to be made across the 4-response groups (CR/PR/SD/PD) using analysis of covariance models with baseline assessments being the covariate in the model.

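### Median OS is the only OS summary named, yet under the trial's own design alternative it would be reached within follow-up with probability of at most about 1% to 3%

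*Combined protocol and SAP*

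**What the plan says.** Objective 2.2.4 reads "To estimate median OS in patients with intermediate-risk HNSCC treated with adjuvant durvalumab with radiotherapy". The analysis plan in section 9.3 repeats it: "Median OS will be estimated using the Kaplan Meier method".

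Endpoint 3.2.3 is broader. It says "OS will be estimated via the Kaplan-Meier method" and "OS is defined as the time from D1 of treatment to death from any cause", without naming the median or any other summary.

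On follow-up, section 5.9 says "All patients will be followed for up to 5 years, or until death, whichever occurs first after removal from study treatment". The 5 years therefore start when treatment stops, not at D1.

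The only efficacy assumption is for DFS. Section 9.2 sizes the trial "to detect a 23% difference in 3 year DFS with 80% power", from 60.8% to 83.8%, with 17 evaluable patients and 18 enrolled. The documents give no OS assumption under durvalumab, no OS rate at a fixed time, no confidence interval for OS and no rule for a median that is not reached.

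**The concern.** A Kaplan-Meier median exists only if the curve falls to 50% during follow-up. The treatment is adjuvant, the assumed DFS is high, and follow-up runs a little over 5 years. The named summary is thus most likely to exist if the drug adds nothing and least likely to exist if it has the effect the trial was sized for.

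At stake is the quality of a prespecified secondary result. If the median is not reached, the report has no prespecified OS point estimate. A fixed-time rate could be read from the curve, but its time point would be chosen after the data were seen.

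**Working it through.** **Inputs.** Historical 10-year DFS 19%, 3-year DFS 60.8% (null) and 83.8% (alternative), N = 17 evaluable and 18 enrolled (section 9.2). Cycles 1-3 take 9 weeks and cycles 4-6 take 3 × 4 = 12 weeks (section 5.2). Follow-up is up to 5 years after treatment (section 5.9). Historical OS is 27% with chemoradiotherapy and 20% with radiotherapy alone (section 1.2). No time point is printed beside those two figures, and I assume 10 years.

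**The plan's own figures.**
- Null rate: 0.19^(3/10) = 0.608, as stated. This conversion is a constant-hazard step.
- Sample size: n = [(z(0.90)·√(0.608 × 0.392) + z(0.80)·√(0.838 × 0.162)) / 0.23]² = 16.55, so 17, as stated. This uses the one-sided alpha of 0.1 in the text. The table prints 0.010 for that column, which would give 39.5, so 40. That mismatch does not affect this point.

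**Length of follow-up from D1.** 5 + 21/52.18 = 5.40 years for a patient who completes treatment.

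**DFS as a lower bound for OS.** Section 3.1 says "DFS is defined as the time from D1 of treatment to time of disease recurrence or death". Death is a DFS event and both clocks start at D1, so OS is at least DFS at every time. DFS events are therefore an upper bound on deaths.

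**Hazards and medians.** h = −ln(S3)/3 and median = ln 2 / h.
- Alternative: h = −ln(0.838)/3 = 0.0589 per year, median 11.8 years. DFS is 74.5% at 5 years and 72.7% at 5.4 years.
- Null: h = −ln(0.608)/3 = 0.1659 per year, median 4.2 years. DFS is 43.6% at 5 years and 40.8% at 5.4 years.
- Historical OS, h = −ln(S10)/10: medians of 5.3 years (27%) and 4.3 years (20%). Reading the figures at 9.4 years instead gives about 5.0 and 4.0 years.

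**Chance that the median is reached.** With complete follow-up, the curve reaches 50% if at least 9 patients die, for N = 17 or 18. The exact binomial probability of 9 or more events is:

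| Scenario | N | by 5 years | by 5.4 years |
|---|---|---|---|
| Alternative (upper bound) | 17 | 1.4% | 2.2% |
| Alternative (upper bound) | 18 | 2.2% | 3.3% |
| Null (upper bound) | 17 | 70% | 78% |
| Historical OS, 27% | 17 | 43% | 52% |
| Historical OS, 20% | 17 | 67% | 75% |

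**Two checks on the alternative.**
- The design hazard ratio is ln(0.838)/ln(0.608) = 0.355. Applied to the historical OS, it gives median OS of 14.9 years (27%) or 12.1 years (20%), and a 0.3% to 1.9% chance of reaching the median (N = 17).
- For true DFS to fall from 83.8% at 3 years to 50% by 5.4 years, the later hazard would have to be ln(0.838/0.5)/2.40 = 0.215 per year. That is 3.6 times the design hazard.

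**What remains reportable.** With 4 deaths among 17 and complete follow-up, S = 13/17 = 0.765 and the log-log 95% interval is 0.488 to 0.904. The lower limit is below 50%, so a finite lower confidence limit for the median exists. With 3 deaths the lower limit is 0.547, so it does not. Under the hazard ratio check above, 4 or more deaths by 5.4 years has a probability of 54% to 70%.

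**The case against.** A reader might infer that the median cannot be reached, that the OS objective cannot be answered, or that OS would yield no number. The documents do not support any of these.

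- The probability under the alternative is small but not zero.
- Endpoint 3.2.3 is the whole Kaplan-Meier curve. Fixed-time rates come from the same data and estimator, so no information is lost.
- An unreached median can be reported with a lower confidence limit. By the calculation above, a finite limit is about as likely as not, or better, even if the drug works.
- The difficulty is conditional. At the historical OS the median is reached about 43% to 75% of the time, and then it is a workable summary.
- The 11.8-year figure extends a constant hazard well beyond year 3, and the protocol never states that assumption in words.
- OS is a descriptive secondary objective here. No test, sample size or decision depends on it.

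All of this stands, and it limits the point to the choice of summary. It does not remove the point. The plan names one OS summary, and that summary is very unlikely to exist in the scenario the trial was designed to find. The constant hazard is the plan's own step, and the conclusion would need a several-fold rise in hazard after year 3 to change.

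**Conclusion.** The point holds in this form: median OS is an unsuitable sole summary if the treatment works. Under the design alternative, median OS is at least 11.8 years, more than twice the roughly 5.4 years of follow-up from D1. The median would be reached with probability of at most about 1% to 3%. If the drug adds nothing, the bound is about 70% to 78% (N = 17).

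This rests on a constant hazard, on DFS events as an upper bound on deaths, and on complete follow-up. With dropout, the curve can cross 50% on fewer deaths once few patients remain at risk, but such a median would be unstable. The historical comparison also assumes that the OS figures in section 1.2 are 10-year values.

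**What to change.** In 2.2.4 and 9.3, replace median OS with Kaplan-Meier OS at 3 and 5 years from D1, each with a log-log 95% confidence interval, as the OS summary. State that the median and its confidence limits will be reported only if the median is reached. Endpoint 3.2.3 needs no change, though naming the two time points there would keep the sections aligned.

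The intervals will be wide: 4 deaths among 17 gives 76% with limits of 49% and 90%. The estimates will nevertheless be available whether or not the drug works.

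The cost is wording only: no added patients, visits or data.

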2.3 Exploratory Objectives

2.3.1 [REDACTED]

[REDACTED]

[REDACTED]

3.0 Criteria for Evaluation / Study Endpoints

3.1 Primary Endpoint

- 3.1.1 3-year DFS will be estimated via the Kaplan-Meier method. DFS is defined as the time from D1 of treatment to time of disease recurrence or death.

3.2 Secondary Endpoints

- 3.2.1 Grade 3-5 acute toxicity will be evaluated according to guidelines from NCI CTCAE, v5.0 and include toxicity from the first day of treatment with immunotherapy until 30 days after completion of concurrent immunotherapy and radiation. Toxicity will include all toxicity attributed to the total study regimen (inclusive of radiation) not just to durvalumab alone.
- 3.2.2 Grade chronic 3-5 toxicity will be evaluated according to guidelines from NCI CTCAE, v5.0 and include toxicity continuing or occurring 30 days after completion of concurrent immunotherapy and radiation, and will be followed for up to 6 months.
- 3.2.3 OS will be estimated via the Kaplan-Meier method. OS is defined as the time from D1 of treatment to death from any cause.

3.2.4 Measure PD-LI expression by immunohistochemistry. Pre-treatment PD-L1 expression will be correlated with disease free survival following treatment of adjuvant durvalumab with radiotherapy

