5.2 Treatment Dosage

This Phase II trial will evaluate the combination of durvalumab with radiation therapy as post-operative therapy in intermediate risk patients with HNSCC. All patients will receive durvalumab and radiation therapy during cycles 1-3. Radiation therapy is administered per standard radiation oncology regimens, on a daily basis and/or as scheduled during a Monday-Friday working week. Radiation therapy is given concurrently with durvalumab during Cycles 1-3. Durvalumab treatment (1500 mg Q3W) Cycles 1-3 are 3-weeks long cycles (total of 9 weeks). Radiation therapy will be delivered at a dose of 2 Gy over 30 fractions totalling a final dose of 60 Gy. Radiation treatment will take 6 weeks (Mon-Fri) or 30 days and will occur for 6 of 9 weeks that define Cycles 1-3. However, due to delays or missed appointments, completion of those 30 fractions may take longer than the allotted 6 weeks and this is allowed. Radiation therapy must be scheduled and completed within Cycles 1-3 and should not extend into Cycle 4. Please refer to Section 6.2 for additional details and allowances.

During Cycle 4-6, only durvalumab 1500mg Q4W will be given.

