8.3 Documentation of non-serious AEs or SARs

For non-serious AEs or SARs, documentation must begin from time of signature of informed consent, throughout the treatment period and including the follow-up period (90 days after the last dose of durvalumab).

During the course of the study all AEs and SAEs should be proactively followed up for each patient. Every effort should be made to obtain a resolution for all events, even if the events continue after discontinuation/study completion.

If a patient discontinues from treatment for reasons other than disease progression, and therefore continues to have tumor assessments, drug or procedure-related SAEs must be captured until the patient is considered to have confirmed PD and will have no further tumor assessments.

The investigator is responsible for following all SAEs until resolution, until the patient returns to baseline status, or until the condition has stabilized with the expectation that it will remain chronic, even if this extends beyond study participation.

Collected information should be recorded in the Case Report Forms (CRF) for that patient. Please include a description of the event, its severity or toxicity grade, onset and resolved dates (if applicable), and the relationship to the study drug. Documentation should occur at least monthly.

Adverse events will be recorded using a recognized medical term or diagnosis that accurately reflects the event (CTCAE 5.0 Meddra terms). AEs will be assessed by the investigator for severity, relationship to the investigational product, possible etiologies, and whether the event meets criteria of an SAE and therefore requires immediate notification to AstraZeneca/MedImmune Patient Safety.

The following variables will be collected for each AE:

- AE (verbatim)
- The date when the AE started and stopped
- The maximum CTCAE grade reported
- Changes in CTCAE grade
- Whether the AE is serious or not
- Investigator causality rating against the IPs (yes or no)
- Action taken with regard to IPs
- Administration of treatment for the AE
- Outcome

In addition, the following variables will be collected for SAEs:

- Date the AE met criteria for SAE
- Date the Investigator became aware of the SAE
- Seriousness criteria fulfilled

- Date of hospitalization
- Date of discharge
- Probable cause of death
- Date of death
- Whether an autopsy was performed
- Causality assessment in relation to study procedure(s)
- Causality assessment in relation to other medication

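### The acute Grade 3-5 toxicity window closes while durvalumab is still being given, and no whole-regimen toxicity rate is planned alongside it

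*Combined protocol and SAP*

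**What the plan says.** Objective 2.2.1 reads "To characterize safety by evaluating Grade 3-4 acute toxicities of adjuvant durvalumab with radiotherapy". The matching endpoint, 3.2.1, uses Grade 3-5 and will "include toxicity from the first day of treatment with immunotherapy until 30 days after completion of concurrent immunotherapy and radiation". It adds: "Toxicity will include all toxicity attributed to the total study regimen (inclusive of radiation) not just to durvalumab alone". Its chronic counterpart, 3.2.2, is to "include toxicity continuing or occurring 30 days after completion of concurrent immunotherapy and radiation, and will be followed for up to 6 months".

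Section 5.2 fixes what concurrent means: "Radiation therapy is given concurrently with durvalumab during Cycles 1-3", and "Cycles 1-3 are 3-weeks long cycles (total of 9 weeks". After that, "During Cycle 4-6, only durvalumab 1500mg Q4W will be given".

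Section 9.3 tabulates the acute Grade 3-5 rate, gives it a confidence interval and uses it to judge a safety criterion. It also reports rates of individual toxicities. For chronic Grade 3-5 toxicity it plans only a table by type and grade.

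Section 8.3 has adverse events documented "throughout the treatment period and including the follow-up period (90 days after the last dose of durvalumab".

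**The concern.** The end of the acute window is tied to the end of the first half of the regimen. Three of the six durvalumab doses come after the concurrent phase, and the window closes during that second half. A patient whose first Grade 3-5 reaction follows dose 6, while still on drug, is counted under chronic toxicity and not in the acute rate.

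This matters because the acute rate is how objective 2.2.1 characterises safety. It is also the quantity that section 1.1 predicts will be lower than with radiotherapy plus cisplatin. No other summary in 9.3 gives the proportion of patients with any Grade 3-5 toxicity over the whole of treatment. The chronic table, for its part, would put new reactions during cycles 4-6 beside late radiation effects without telling them apart.

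**Working it through.** **Inputs.** Cycles 1-3 last three weeks each and cycles 4-6 four weeks each (5.2, 5.2.1). Radiotherapy is 30 weekday fractions and must finish within cycles 1-3 (5.2). The acute window ends 30 days after the concurrent phase (3.2.1). Enrolment is 18 (9.2). Day 1 is C1D1, with no delays.

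**The plan's own figures.** 3 cycles × 3 weeks = 9 weeks (days 1-63), and 30 fractions ÷ 5 per week = 6 weeks. Both agree with 5.2.

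**Dose days.** 1, 22, 43, 64, 92, 120. Cycle 6 ends on day 120 + 28 − 1 = 147. Cycles 4-6 run from day 64 to day 147, which is 84 days.

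**When the window closes.** The plan does not say which day completes concurrent treatment, so each reading is shown. Close = end + 30.

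| Concurrent phase ends with | End day | Window closes | Days inside after dose 4 | Dose 5 (day 92) | Dose 6 (day 120) | Treatment days outside, of 147 | Of the 84 days of cycles 4-6 |
|---|---|---|---|---|---|---|---|
| Last fraction, Monday start | 40 | 70 | 6 | outside | outside | 77 (52%) | 92% |
| Six full weeks | 42 | 72 | 8 | outside | outside | 75 (51%) | 89% |
| Dose 3 | 43 | 73 | 9 | outside | outside | 74 (50%) | 88% |
| End of cycle 3 | 63 | 93 | 29 | inside by 1 day | outside | 54 (37%) | 64% |

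Dose 5 is inside only if the concurrent phase ends on day 62 or 63 (92 − 30 = 62). Dose 6 would need an end on day 90 (120 − 30), which the schedule does not permit. Section 12.1.1 allows dose holds; a hold in cycles 4-6 would move more exposure outside.

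**What collection already covers.** 90 days after dose 6 is day 120 + 90 = 210, so the data in 8.3 run 117 to 140 days past the close of the acute window.

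**Weight of one patient.** 1 ÷ 18 = 5.6 percentage points.

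**Illustration only.** Suppose a fraction q of patients with no acute event has a first Grade 3-5 event after the window. The whole-regimen rate is 1 − (1 − a)(1 − q), where a is the acute rate. The documents give no value for q; 5% to 20% is assumed here. With a = 34.4%, the radiotherapy-alone rate in 1.2.1, the result is 37.7% to 47.5%, or 0.6 to 2.4 more patients of 18. With a = 77%, the cisplatin rate in 1.2.1, it is 78.2% to 81.6%, or 0.2 to 0.8 more patients.

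**The case against.** The strongest reply is that nothing is lost. The acute and chronic windows adjoin, later events are dated and collected, and 9.3 tabulates them. That stands. A reader might infer that toxicity from cycles 4-6 goes unreported, and the documents do not support that. What is missing is a per-patient rate across the regimen.

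A reader might also take the reference in 3.2.1 to the total regimen as a promise about time, and so find a contradiction. Read whole, "Toxicity will include all toxicity attributed to the total study regimen (inclusive of radiation) not just to durvalumab alone" says which causes count: radiation effects as well as drug effects. It does not say that the window spans cycles 4-6.

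A window tied to radiotherapy is also a reasonable match to the acute rates of 34.4% and 77% in 1.2.1. The documents do not give that as the reason, but it is a good argument for keeping the window.

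Finally, one could start chronic toxicity only after the on-treatment period, at about day 210. That would relabel radiation effects arising in the preceding months as on-treatment. It could also leave little chronic follow-up. Section 3.2.2 does not say when its six months begin. Counted from the end of the concurrent phase, with six months taken as 183 days, they end on day 223 to 246, only 13 to 36 days after day 210. This objection stands, and the chronic window should not be moved.

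**Conclusion.** The gap in coverage is real under every reading of the window. Dose 6 is always outside, dose 5 is outside or inside by a single day, and 37-52% of the nominal treatment period is uncovered. First Grade 3-5 events in that time cannot enter the one toxicity rate that has a planned interval and a safety criterion, and no whole-regimen rate exists beside it.

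The result rests on the nominal calendar and on the meaning of concurrent in 5.2. It does not rest on any assumption about when reactions occur. A reader might go further and compute a missed share of durvalumab-related events: 1 − 93/150 = 38% to 1 − 70/150 = 53%, if onset is even from day 1 to 30 days after dose 6. The documents give no onset distribution, and earlier onset would lower that share. It also concerns drug-related events only, whereas the endpoint counts patients with any regimen toxicity, and a patient with an acute event is counted whatever follows. The number of patients affected therefore cannot be derived.

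The primary disease-free survival endpoint is untouched. This is an inexpensive improvement to the safety reporting and does not call for redefining the endpoints.

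**What to change.** - **Add** to 3.2.1 and 9.3 the proportion of treated patients with any Grade 3-5 toxicity from C1D1 through 90 days after the last durvalumab dose, with a confidence interval, as the whole-regimen safety result for 2.2.1.
- **Keep** the present window, labelled *concurrent-phase acute rate*, for the comparison with radiotherapy plus cisplatin. State which day completes the concurrent phase.
- **Leave** the chronic window in 3.2.2 as it is, but split its table into three groups: events that began in the acute window and persisted; new-onset events during cycles 4-6 or within 90 days of the last dose; and later events.

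No new data are needed, since 8.3 already collects start dates and grades over this period. The cost is one extra summary and a headline toxicity rate that may be somewhat less favourable.
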